#### 3. STUDY DESIGN

#### 3.1. DESIGN

The design of this study is sequential mixed methods with a nested pilot Randomized Controlled Trial (RCT); three interrelated phases, as:

**Phase one**: A survey design will be used to identify cardiac patients' medication adherence/non-adherence patterns and the factors that are most strongly associated with their medication non-adherence. The purpose of the survey is to gather quantitative data about medication adherence, patient behaviours, beliefs and other factors associated with medication non-adherence as well as

patients' demographic data. Paper based questionnaires will be used. The questionnaires will be self-administered, simple and easy to complete, and suitable for participants with low literacy.

Phase two: Semi-structured interviews will be used to gather descriptive qualitative data to explore the phenomenon of cardiac patients' adherence to medications and how they respond to factors that affect medication adherence. Semi-structured interviews will be used to explore views of patients about their cardiac medications, and factors that influence their medication adherence. Semi-structured interviews were chosen because this is a flexible method of collecting self-report data and allows the researcher to prepare questions ahead of time (Cohen and Crabtree, 2006). Semi-structured interviews will allow participants to cover all the study questions and by encouraging participants to talk freely about issues related to their medication adherence and tell stories in their own words, this method provides as much detail as the researchers wish (Polit and Beck, 2004). Semi-structured in-depth interviews will involve open-ended, direct, and verbal questions to elicit detailed narratives and stories building on an interview guide (Whiting, 2008). This will provide in-depth understanding, supplement and explain quantitative results from Phase one.

Information generated from phases one and two will be used to identify participants eligible to take part in the pilot trial phase, and synthesized to inform motivational interviewing processes aiming at addressing individual patients' medication adherence-related needs and support patients' adherence to their cardiac medications;

Pilot trial phase: Patients identified as non-adherent based on the result of exploratory phases (phase one and two) will be invited to participate in the pilot randomised controlled trial phase. This pilot RCT will test the effectiveness of a multifaceted intervention, comprising motivational interviewing (MINT) plus text message reminders, to influence the adherence of patients to their cardiac medications. The RCT will compare the effect of a multifaceted intervention with current standard care to enhance medication adherence outcomes. The control group will receive the standard usual care cardiac rehabilitation program and they will complete the baseline and follow-up questionnaires.

#### 3.2. STUDY GROUPS

Participants will be cardiac patients referred to a cardiac rehabilitation program following their hospital admission for acute cardiac events; those participating in the pilot trial phase will be randomly allocated to receive either the intervention plus usual care or usual care only.

Version 2: 20/05/2016 ------ Page 9 of 42

**Intervention group:** Participants in the intervention group will receive usual care plus behavioural counselling about medication adherence using MINT techniques and text message reminders. Each patient will receive approximately 30-40 minutes of a single MINT counselling session following recruitment (Appendix D) (Ma et al., 2014). The core of motivational interviewing is for the counsellor to be simultaneously sympathetic and supportive, as well as directive in moving patients toward change by strengthening their own reasons for change (Levensky et al., 2007). As part of the MINT counselling, the researcher has the opportunity to provide information that the patient may need or to explore some of the barriers that keep this patient from adherence to medications (Dart, 2010). Text message reminders (TM) (Appendix E) will be sent to these participants: one text message daily for two weeks, then on alternate days for two weeks and then on a weekly basis for the next 6 months (Wald et al., 2014). The content of the text message reminders will vary according to the patients' non-adherence factors. An example of the text message reminder is:

The researchers will use a structured MINT counselling script (Appendix D) designed for patients with low adherence to medications, with each session tailored to the medication adherence characteristics of the individual patient (Dart, 2010). All MINT sessions will be audio taped and reviewed by a clinician qualified in MINT to ensure fidelity to the technique (Ma et al., 2014).

**Control group**: Patients randomised to the control group will receive standard care alone for the study period. They will be contacted at baseline and 6 months to complete the same measurements and interviews as the intervention group.

#### 3.3. NUMBER OF PARTICIPANTS

The researcher will sample of a cohort participants referred to cardiac rehabilitation for phases one and two until adequate numbers have been recruited for pilot trial phase. To calculate the sample size for the study, the researcher used values for the means (M) and standard deviation (SD) based on data from Ma et al. (2014) using the following formula:

Cohen's  $d = M1 - M2 / \sigma$  pooled, where  $\sigma$  pooled =  $\sqrt{(\sigma 12 + \sigma 22) / 2}$ 

M1= means for group  $1 = 29.72\pm3.46$ 

M2= means for group  $2 = 25.30 \pm 3.11$ 

Version 2: 20/05/2016 ----- Page 10 of 42

The resultant value for 2 sided test for alpha = 0.05, with power = 0.80, is a sample size of 9 for each group. Based on the results of the sample size calculation formula, 9 participants with complete data in each group will be required to detect a difference in the means of 4.42 points for the primary outcome at 6 months, assuming a common standard deviation of 3.285, with a power of  $\beta = 80\%$  and a two-sided  $\alpha$  value of 0.05. Assuming up to 50% attrition, a total of 28 participants will be recruited for pilot trial phase.

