Non-adherence to medications will be assessed by the **Medication Adherence Questionnaire** (**MAQ**) designed to measure medication adherence behaviour and barriers such as forgetfulness, carelessness, adverse effects and efficacy. MAQ includes simple four-item dichotomous questions, scoring one point for each yes response; total scores are categorised as: 0 point indicating high; 1-2 points medium, and 3-4 points low medication adherence behaviour.

The Adherence to Refills and Medications Scale (ARMS) will be used to determine the patient medication adherence behaviour in terms of self-regulation. The ARMS comprises a 12-item scale with the first 8-item medication taking subscale assessing correct self-administration ability for the prescribed regimen. The next 4-item prescription refill subscale assesses the patient's ability to refill medications on schedule. Each item is scored on a four point scale ranging from l=

Version 2: 20/05/2016 ----- Page 15 of 42

none of the time to 4= all the time. The higher numbers on the scale demonstrate patient's better ability to refill medications on schedule.

The Belief about Medicine Questionnaire (BaMQ) elicits information on patients' beliefs about their medicines where they may relate to adherence. It identifies whether the patient holds beliefs that their medicines are necessary or if they have concerns about their medicines. The study will use the short version of the BaMQ (the 8-item) developed by Horne et al., 1999. This version is composed of four subscales containing two items each, and assessing: General Harm; General Overuse; Specific Necessity; and Specific Concerns. Respondents indicate their degree of agreement with each statement on a five point Likert scale, ranging from l=strongly disagree to 5=strongly agree. The lower numbers on the scale demonstrate the patient's strong beliefs about taking medications. Scores are summed to give a total score, with higher scores indicating more positive beliefs. The focus of the BaMQ, is identification of barriers to medication adherence, contributing to comprehensive evaluation of the drivers behind medication adherence.

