#### 5.4. RECRUITMENT AND SCREENING

Patients identified as 'non-adherent' to at least one of their cardiac medications based on the result of exploratory phases (Phase One and Phase Two) will be invited to participate in this pilot

Version 2: 20/05/2016 ----- Page 18 of 42

randomised trial phase. Participants will be assessed as adherent or non-adherent based on the response to the Medication Adherence Questionnaire (MAQ). Patient with a total score of 1-2 will be considered as "adherent", and those with a total score of 3-4 as "non-adherent". At conclusion of the interview (Phase Two), eligible participants who are identified as "non-adherent" will be informed about Phase 3, the pilot RCT trial phase.

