#### 5.6. RANDOMISATION PROCEDURE: PILOT TRIAL PHASE ONLY

In pilot trial phase participants will be randomly allocated to receive either multifaceted intervention comprising current standard care plus motivational interviewing (MINT) follow by text messages or current standard care alone. Participants will be randomised after they have consented to participate in the trial phase, so that the decision to participate has no bearing on which arm of the trial they are allocated to. A random sequence will be generated by computerised random number generator and using permutated blocks in order to assure equal numbers in each arm, balanced at set intervals at 1:1 ratio.

Version 2: 20/05/2016 ----- Page 19 of 42

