#### 8. STATISTICAL CONSIDERATIONS

#### Sample Size or Power Calculation

Sample size for the RCT was calculated based on data from Ma et al. (2014). The researcher predefined and utilised the value for the means (M) and standard deviation (SD) based on Ma et al. using the following formula:

Cohen's 
$$d = M_1 - M_2 / \sigma_{\text{pooled}}$$
, where  $\sigma_{\text{pooled}} = \sqrt{[(\sigma_1^2 + \sigma_2^2) / 2]}$   
 $r_{Y\lambda} = d / \rightarrow square\ root\ (d^2 + 4)$ 

M1= means for group  $1 = 29.72 \pm 3.46$ 

M2= means for group  $2 = 25.30 \pm 3.11$ 

The resultant value for 2 sided test for alpha = 0.05, with power = 0.80, is a sample size of 9 for each group. The formula for calculation of the sample size is set out in Box 1 and for this study produced:

n= 
$$2[(a+b)^2\sigma^2)$$
]  
 $(\mu_1-\mu_2)^2$ 

$$n=2[(1.96+0.842)^2 3.285^2)]$$

$$(29.72-25.3)^2$$

$$N = 2[(2.802)^{2} 3.285^{2})]$$
 =  $2[7.8512 \times 10.7912]$  =  $2[84.7239]$  =  $169.448 = 8.67$   
19.5364 19.5364 19.5364 19.5364

9 participants per group.

Box 1: Formula for a continuous outcome and equal sample sizes in both groups, assuming: alpha = 0.05 and power = 0.80 (beta = 0.20)

n= the sample size in each of the groups  $\mu_1=$  population mean in treatment Group 1  $\mu_2=$  population mean in treatment Group 2  $\mu_1-\mu_2=$  the difference the investigator wishes to detect  $\sigma^2=$  population variance (SD) a= conventional multiplier for alpha = 0.05 b= conventional multiplier for power = 0.80  $\frac{n=2\left[(a+b)^2\sigma^2\right]}{\left(\mu_1-\mu_2\right)^2}$ 

Allowing for 50% loss to follow-up, based on these calculations, a sample size of 28 participants for both groups will be needed in the pilot trial phase to ensure an adequate response rate for statistical analysis.

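### The sample-size inputs are on an unnamed scale and tied to no named primary outcome, so they do not support 80% power for the outcome claimed

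*Protocol*

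**What the plan says.** Protocol section 3.3 takes two means and SDs from a cited trial (29.72±3.46 and 25.30±3.11) and concludes: "The resultant value for 2 sided test for alpha = 0.05, with power = 0.80, is a sample size of 9 for each group". It says these 9 completers are "required to detect a difference in the means of 4.42 points for the primary outcome at 6 months", "assuming a common standard deviation of 3.285". Section 8 repeats the calculation. The Summary repeats the alpha, the power and the total of 28. None of the three says which questionnaire the means were measured on.

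Sections 2.2 and 9 define the pilot trial's primary outcome as adherence or non-adherence at six months, together with (or as an alternative to) change in adherence scores from baseline. Neither names an instrument. Section 9 lists five questionnaire scores for the t-tests (MSSS, MAQ, ARMS, BaMQ and the self-efficacy scale) and ranks none of them.

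The only rule that sorts patients into adherent and non-adherent is in section 5.4: "Participants will be assessed as adherent or non-adherent based on the response to the Medication Adherence Questionnaire (MAQ"). Section 5.3.1 describes that instrument: "MAQ includes simple four-item dichotomous questions, scoring one point for each yes response".

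**The concern.** A power statement has meaning only for a given outcome on a given scale. Here the difference is stated in points and attached to the primary outcome, but the plan names neither the instrument for that outcome nor the scale of the borrowed values. Most of the outcomes the trial could mean cannot produce those values.

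The sentence is also the justification for the number recruited. If it stands, a null result on the adherence rate or the MAQ score could be read as coming from a comparison with 80% power, when no calculation in the protocol supports that for either measure.

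**Working it through.** **1. Reproducing the plan's figure.** Section 8 uses n = 2(a+b)²σ²/(μ₁−μ₂)² with a = 1.96, b = 0.842, σ = 3.285 and a difference of 29.72 − 25.30 = 4.42.

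- (2.802)² = 7.8512; 3.285² = 10.7912; 4.42² = 19.5364.
- n = 2 × 7.8512 × 10.7912 / 19.5364 = 8.67, so 9 per group, as stated.
- The 3.285 is the simple average of the two SDs. The pooled formula printed in the protocol gives √[(3.46² + 3.11²)/2] = 3.290, which also leads to 9.

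The arithmetic is sound. It depends only on the ratio 4.42/3.285 = 1.35.

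**2. Can the inputs occur on this trial's outcomes?** The ranges follow from the scoring in section 5.3.1.

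| Candidate outcome | Possible range | Can it hold means of 25.30 and 29.72? |
|---|---|---|
| Adherence rate | proportion | No; a formula for means does not apply and no proportions are assumed |
| MAQ score (4 yes/no items) | 0 to 4 | No |
| MASES-R (mean of items scored 0–3) | 0 to 3 | No |
| MSSS (mean of items scored 0–4) | 0 to 4 | No |
| ARMS sum (12 items scored 1–4) | 12 to 48 | Yes, by range |
| BaMQ sum (8 items scored 1–5) | 8 to 40 | Yes, by range |

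On the MAQ the largest possible difference between two group means is 4.0, below 4.42. The largest possible SD is 2 (half of all scores at 0 and half at 4). As a sample SD with n = 9 it is 4 × √[(4 × 5)/(9 × 8)] = 2.11. Both are below 3.285. Using change from baseline does not rescue the inputs: with equal baseline means in the two arms, the difference in mean change equals the difference in six-month means and is again at most 4.0.

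**3. What 28 recruits can detect on a continuous score.** Two-sided t-test, alpha 0.05, 80% power, noncentral t, equal arms (section 5.6):

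| Per arm | Basis | Detectable effect |
|---|---|---|
| 14 | all 28 complete | 1.10 SD |
| 9 | the plan's completer target | 1.41 SD |
| 7 | 50% of 28 lost | 1.63 SD |

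With 9 per arm, the t-test named in section 9 has 76.4% power for 1.35 SD. The 81.4% that corresponds to the plan's formula is a normal approximation.

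The protocol gives no MAQ SD. If the SD is assumed to lie anywhere from 0.5 to 2.0, the detectable MAQ difference is 0.55 to 2.20 points with 14 per arm, 0.70 to 2.81 with 9, and 0.82 to 3.26 with 7. That spread is too wide for any single figure in MAQ points to be relied on.

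**4. If the outcome is the adherence rate.** The protocol states no proportions, so those below are assumed for illustration. Two-sided Fisher test, 14 per arm, no loss, by full enumeration:

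| Control v intervention | Power |
|---|---|
| 20% v 50% | 26% |
| 20% v 70% | 65% |
| 20% v 80% | 84% |

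**The case against.** A reader might infer that the sample size is impossible for this trial's primary outcome, because 4.42 points exceeds the whole range of the MAQ. The protocol does not support that. It fixes the MAQ as the classifier at trial entry and does not name it as the six-month outcome. The ARMS is also described as a measure of adherence behaviour, and an ARMS or BaMQ sum could hold the inputs.

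A reader might also infer that the plan has no idea what effect it can detect. That goes too far as well. Sections 3.3 and 8 set out Cohen's d, and the inputs imply a known standardised target of about 1.35, which could apply to any continuous score.

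The trial is a labelled pilot serving a secondary objective, and correcting the statement changes neither allocation nor data collection. The 7-per-arm row reflects the attrition allowance, which is a separate question and adds no weight here.

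All of this stands, and it narrows the point. It does not remove it. The protocol goes beyond d: it claims power for a difference in points on the primary outcome. A standardised effect does not carry over to a binary rate, and nothing in the protocol shows why 1.35 SD is plausible on whichever score is meant. A statistical analysis plan could name the instrument later, but the claim made here would still have no support in the protocol.

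**Conclusion.** The concern holds in this limited form. The 9 per group is computed correctly from the stated inputs, but those inputs are on an unnamed scale and are tied to no named outcome. They cannot apply to the adherence rate, the MAQ score, or the MASES-R or MSSS means. They could apply to an ARMS or BaMQ sum, which the protocol designates neither as primary nor as the source scale. What the calculation supports is roughly 1.35 SD on some continuous score, not 80% power for the primary outcome as stated.

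The range argument rests only on the scoring rules in section 5.3.1. The detectable effects assume equal arms, a two-sided 5% t-test and 80% power. The Fisher powers rest on assumed proportions and no loss to follow-up.

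**What to change.** - In sections 3.3 and 8, withdraw the claim of 80% power for 4.42 points on the primary outcome, and bring the alpha and power line in the Summary into agreement.
- Name one primary outcome and the instrument that measures it.
- If it is a continuous score, state what 28 recruits can detect in SD units: 1.10 with 14 per arm, 1.41 with 9 and 1.63 with 7. Give scale points only with a sourced SD, or over a wide assumed range.
- If it is the adherence rate, state the assumed proportions and the power for them, as in the illustration above.
- If the source values are kept, name their scale and make that scale the primary outcome.

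The cost is redrafting the sample-size text. Enrolment stays at 28. The stated sensitivity becomes less favourable.

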#### Sample size calculation:

- With alpha = 0.05 (2sided), power= 0.80 (beta= 0.20).
- With consecutive sampling and allowing for 50% loss to follow-up.
- A sample size of 28 participants for both groups will be recruited (Ma et al. 2014).

**Recruitment and screening**: Patients referred to Cardiac Rehabilitation at POWH will be screened by the Clinical Nurse Consultant (CNC) as they attend their first session. For Phases One and Two, eligible patients will:

- Have an established diagnosis of cardiac disease by their physician;
- Will have been prescribed at least one cardio-protective medication at least 7 days prior to recruitment;
- They must have primary responsibility for taking their medication themselves (i.e. whilst a carer may play a role in supporting or promoting medication taking, they should not be identified as being accountable for ensuring the patient's adherence to their medication schedule);
- Patients must not be clinically judged as affected by cognitive impairment and must be able to speak, read and understand English, own a personal mobile phone, and be able to receive and reply to phone calls and text messages.

All patients recruited will complete a paper-based survey (phase one) and a brief face to face interview (phase two).

For the Pilot Trial Phase:

Participants identified as 'non-adherent' to at least one of their cardiac medications, based on the
result of exploratory phases of the study (survey and interview), will be invited to participate in
the final pilot randomised trial phase.

Patients recruited to the pilot trial phase will be randomly allocated to either an intervention or control arm.

**Intervention:** Participants in the intervention group will receive usual care plus behavioural counselling about medication adherence using motivational interviewing (MINT) techniques and text message reminders.

**Control group**: will receive the usual cardiac rehabilitation program.

**Analysis plan:** Phase one: Descriptive statistics; Phase two: thematic analysis; Pilot trial Phase: descriptive statistics and inferential data analysis.

**Duration of the study:** The total duration of the study will be 12 months (six months for recruitment and six months participation for each participant recruited).

Version 2: 20/05/2016 ------ Page 4 of 42

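### At the stated 50% attrition, 28 recruits leave 7 completers per arm, not the 9 required, and t-test power is about 64% rather than 80%

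*Protocol*

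**What the plan says.** Section 3.3 sets the target in terms of completers: "9 participants with complete data in each group will be required". The planning values behind it are a 4.42-point difference on the six-month primary outcome and an SD of 3.285 in both arms, at two-sided 5% significance and 80% power. It then moves to recruitment: "Assuming up to 50% attrition, a total of 28 participants will be recruited for pilot trial phase".

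Section 8 works the same formula through to 8.67, rounds up to 9 per group, and concludes: "Allowing for 50% loss to follow-up, based on these calculations, a sample size of 28 participants for both groups will be needed". The Summary, under Sample size calculation, lists the same significance level and power, then "With consecutive sampling and allowing for 50% loss to follow-up", then 28 for both groups.

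Section 5.6 fixes 1:1 allocation in permuted blocks. Section 9 names the independent-samples t-test for the between-group comparison.

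**The concern.** The 9 per arm are explicitly participants with complete data, so 28 must be the number that still leaves 18 after the stated loss. Half of 28 is 14. The sample size therefore does not have the property claimed for it.

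This matters because the protocol chose to power the pilot. Section 3.1 says it will test effectiveness, section 2.2 describes it as pilot-testing a hypothesis, and section 9 plans inferential tests. A reader is led to believe that the trial keeps 80% power after losing half its participants. If that loss occurred, a null result would be taken as stronger evidence than it is, even against the very large effect assumed. The figure 28 is also the planned sample size in the Summary and the basis of the six-month recruitment estimate in section 3.5.

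**Working it through.** **Inputs, all from the protocol**
- Means 29.72 and 25.30, difference 4.42; common SD 3.285 (sections 3.3 and 8)
- Two-sided alpha 0.05, power 0.80 (Summary, 3.3, 8)
- Completers required: 9 per arm (3.3, 8)
- Attrition: 50% (Summary, 8), given as a ceiling in 3.3
- Recruits: 28 in total (Summary, 3.3, 8), allocated 1:1 (5.6), so 14 per arm
- Test: independent-samples t-test (9)

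**Step 1. Reproduce the 9 per arm.**
n = 2(1.96 + 0.842)² × 3.285² / 4.42² = 169.448 / 19.5364 = 8.67, rounded up to 9. The protocol's figure reproduces.

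**Step 2. Reproduce the 28.**
- Multiplying by (1 + loss): 9 × 1.5 = 13.5, rounded up to 14 per arm, 28 in total. This matches.
- Dividing by (1 − loss): 9 / 0.5 = 18 per arm, 36 in total. This does not match.

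The figure 28 is thus consistent with completers having been multiplied by 1.5 where they should have been divided by 0.5.

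**Step 3. Completers left from 28.**
28 × 0.5 = 14, or 7 per arm if the loss is equal between arms. The shortfall is 2 per arm.

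**Step 4. Power.**
The standardised difference is d = 4.42 / 3.285 = 1.3455. For the t-test, power comes from the noncentral t distribution with 2n − 2 degrees of freedom and noncentrality d√(n/2). At n = 7 the noncentrality is 2.517 and the critical value is 2.179 on 12 degrees of freedom.

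| Completers per arm | t-test | Protocol's normal approximation |
|---|---|---|
| 7 | 63.8% | 71.1% |
| 9 | 76.4% | 81.4% |
| 10 | 81.2% | 85.3% |
| 14 (no loss) | 92.9% | 94.5% |

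Using the root-mean-square SD of 3.46 and 3.11, which is 3.290, changes the t-test figure at 7 per arm only to 63.7%.

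**Step 5. Attrition that 28 can absorb.**
- For 9 per arm: 1 − 18/28 = 35.7%
- For 10 per arm, the smallest number at which the t-test reaches 80%: 1 − 20/28 = 28.6%

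**Step 6. Recruits needed at 50% loss.**
- On the protocol's formula: 18 / 0.5 = 36
- For the t-test: 20 / 0.5 = 40

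**Step 7. Allowing for chance in who drops out.**
Suppose each participant is lost independently with probability 0.5. The number of completers per arm is then binomial (14, 0.5). The chance of at least 9 in one arm is 3473/16384 = 0.212, and in both arms 0.212² = 4.5%. Averaging t-test power over all splits gives about 61%.

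**The case against.** Five points can be made for the plan.

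1. **The fall from 80% to 64% is not all due to the attrition slip.** This stands. Like for like, the slip costs about 10 points on the protocol's formula (81.4% to 71.1%) and about 13 on the t-test (76.4% to 63.8%). The rest comes from using a normal-approximation formula for a t-test in a very small sample. That is a common convention and the protocol applies it correctly, so it is a refinement and secondary to the main error.

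2. **In section 3.3, 50% is a ceiling.** Seven per arm is therefore the worst case planned for, and with full retention power is 92.9%. This limits the point without removing it: an allowance exists to cover its stated limit, and neither section 8 nor the Summary describes 50% as a ceiling. The independent-dropout figures in Step 7 also treat 50% as the expected loss and are illustrative only.

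3. **No single sentence says outright that 28 gives 80% power after 50% loss.** That is literally true. Section 3.3 attaches the power to the 9 completers, section 8 justifies 28 as giving an adequate response for analysis, and the Summary lists the items as separate bullets. But the three accounts have no other purpose than to link them, and section 8 says that 28 follows from the calculations.

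4. **The power figures depend on an effect taken from a cited study, on a scale the protocol does not name.** This stands as a caveat. The 4.42-point difference cannot be on the Medication Adherence Questionnaire, which runs from 0 to 4. The 64% is conditional on d = 1.35; the mismatch between 28 and 36 is not.

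5. **A pilot need not be powered.** That is correct in general, but this one makes a formal power statement, which should then be right.

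**Conclusion.** The concern holds. At the stated 50% attrition, 28 recruits give 7 completers per arm against the 9 required, and 36 would be needed to meet the protocol's own target. Power at that attrition is 63.8% for the planned t-test and 71.1% on the protocol's formula, so it is below 80% either way.

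The recruitment error rests only on the stated 9 per arm, the 50% allowance and 1:1 allocation. The power figures further assume the protocol's difference and SD, equal loss in the two arms, and attrition at the stated limit. It should be corrected before the protocol is relied on, because it concerns the headline sample size and appears in three places.

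**What to change.** Keep 28 and correct the statement in the Summary, section 3.3 and section 8. Suggested wording:

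> Recruiting 28 participants leaves 9 completers per arm if attrition is at most 35%, and 10 per arm, the number the t-test needs for 80% power, if attrition is at most 28%. At 50% attrition 7 per arm remain and t-test power is 64% for a standardised difference of 1.35.

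The sentence should also name the scale to which the standardised difference refers.

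The cost is wording in three places and a less favourable statement of power or tolerated attrition. Recruitment, allocation and analysis do not change.

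If the sponsor prefers to keep both the 50% allowance and 80% power, the recruitment target becomes 36 on the protocol's formula or 40 for the t-test, that is 8 or 12 more participants. The six-month recruitment estimate in section 3.5 would then need to be reconsidered.
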